#### 4.2.3.2 Derivations

Binary endpoints of resolution of NASH and fibrosis improvement will be derived from datasets transferred from the histopathology vendor. These datasets will include NAS components, NAS and fibrosis stages, but not derived endpoints (such as NASH resolution). Final scores for each NAS component and fibrosis stage based on the process described in Central Histopathology Review Charter will be used to derive variables for analysis. Because resolution of NASH allows steatosis score of any degree (from 0 to 3), if the steatosis score is not evaluable, resolution of NASH will still be concluded if there is a ballooning score of 0 and an inflammation score of 0 to 1.

Analysis of absolute change from baseline will use the post-baseline value minus the baseline value.

Analysis of percent change form baseline will use the natural log-transformed post-baseline value minus the natural log-transformed baseline value (log ratio). Calculation of summary measures with least squares mean (LSMEAN) or least squares mean difference (LSMD) values from analysis of covariance (ANCOVA) or mixed model for repeated measures (MMRM) using log-transformed values is described in Table 9.

Table 9 Formula for ANCOVA or MMRM Using Log-transformed Values

Quantity	Computation Method
Estimate for Percent Change from Baseline	$100 \times [\exp(LSMEAN \text{ change from baseline in natural} \\ logarithm) - 1]$
LCL for Percent Change from Baseline	$100 \times [exp(LCL \text{ for LSMEAN change from baseline in } \\ natural logarithm) - 1]$

Table 9 Formula for ANCOVA or MMRM Using Log-transformed Values

Quantity	Computation Method
UCL for Percent Change from Baseline	$100 \times [exp(UCL \text{ for LSMEAN change from baseline in } \\ natural logarithm) - 1]$
Estimate for Ratio Change from Baseline, Cotadutide relative to Control	exp(LSMD in mean change from baseline in natural logarithm)
LCL for Ratio Change from Baseline, Cotadutide relative to Control	exp(LCL for LSMD in change from baseline in natural logarithm)
UCL for Ratio Change from Baseline, Cotadutide relative to Control	exp(UCL for LSMD in change from baseline in natural logarithm)

ANCOVA, analysis of covariance; LCL, lower confidence limit; LSMEAN, least square mean; MMRM, mixed model for repeated measures; exp, exponent; UCL, upper confidence limit.

If both direct and calculated LDL lab codes are entered, they will be combined into a single parameter for analysis.

Age post-screening is required for some endpoint derivations and will be based on the latest date of collection for values of components used to determine the score. Age at screening and year of birth is collected directly on the CRF; month and day of birth will not be entered. The age at screening used for analysis will be the directly entered value. For determination of age post-screening, a complete birth date needs to be imputed and the following algorithm will be used:

• If (age at screening) = (year of screening) – (year of birth), then impute the month and day of birth date as the month and day of the screen date. If screening falls on 29 February, then impute as 28 February instead.

If (age at screening) = (year of screening) – (year of birth) – 1, then impute the month and day of birth date as the month and day of the day after the screen date. If that date falls on 29 February, then impute as 1 March instead.

Agile-3+ will be calculated as described in (Sanyal et al 2023):

- Agile  $3+=\frac{e^{Xb}}{1+e^{Xb}}$
- Where Xb =  $-3.92368+2.29714 \times \ln(LSM) 0.00902 \times \text{platelets} 0.98633 \times (AST/ALT ratio)^{-1} +1.08636 \times \text{Diabetes status} 0.38581 \times \text{Sex} + 0.03018 \times \text{Age}$
- Variables: LSM in units of kPa, platelets in units of  $10^9$ /L, AST/ALT ratio based on AST and ALT in any consistent units, age in units of years, diabetes status: yes = 1, no = 0 and sex: male = 1, female = 0

Values of FAST used for analysis will be calculated based on values of LSM, CAP, and AST in the database (LSM and CAP from FIBSCAN module and AST from central laboratory) as described in (Newsome et al 2020):

- $FAST = \frac{e^{Xb}}{1+e^{Xb}}$
- Where  $Xb = -1.65 + 1.07 \times ln(LSM) + 2.66 \times 10^{-8} \times CAP^3 63.3 \times AST^{-1}$
- Variables: LSM in units of kPa, CAP in units of dB/m, and AST in units of IU/L

BARD will be calculated as described in (Harrison et al 2008), as a score between 0 and 4 where:

- 1 point is assigned for BMI  $\geq$  28 kg/m^2
- 2 points are assigned for an AST/ALT ratio  $\geq 0.8$
- 1 point is assigned for T2DM

# 4.2.3.3 Handling of Dropouts and Missing Data

A post-baseline liver biopsy is planned for each participant at Week 48. Participants who discontinue study intervention early will have an early discontinuation visit. Participants will be encouraged to have the biopsy at Week 48 as planned in the CSP schedule of activities. Participants who are unwilling or unable to wait until Week 48 will have the biopsy procedure as part of the early discontinuation visit if they have received study intervention for at least 36 weeks. Participants who have not been on study intervention for at least 36 weeks will not have a biopsy at the early discontinuation visit.

Unless stated otherwise, the following rules will be used for missing data in exploratory endpoints:

- For biopsy endpoints analysis using the FAS analysis set, will impute missing observations as non-responders while analysis using the PP analysis set will exclude participants with missing data.
- Missing observations for ordinal endpoints will not be imputed, unless otherwise stated.
- Missing observations for continuous endpoints for analyses including multiple postbaseline timepoints will not be imputed.
- Missing observations for continuous endpoints for analyses including only a single post-baseline timepoint will be imputed using multiple imputation (monotone regression) separately by randomized treatment arm with stratification variables (baseline fibrosis stage and T2DM status) and baseline measurement for the endpoint as independent variables. If an issue is encountered for fitting an imputation model (eg, collinearity with intercept), a simplified imputation model may be used.

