# 7 DISCONTINUATION OF STUDY INTERVENTION AND PARTICIPANT DISCONTINUATION/WITHDRAWAL

# 7.1 Discontinuation of Study Intervention

It may be necessary for a participant to permanently discontinue (definitive discontinuation) study intervention. Participants who discontinue study intervention early will have an early discontinuation visit as described in the SoA (Section 1.3). After the early discontinuation visit, participants will be encouraged to remain in the study for all remaining visits and study procedures as outlined in the SoA, with the exception of the urine pregnancy test, dispensation of study intervention and Instructions for Use, and PK sampling. Participants will be encouraged to have the biopsy at Week 48 as planned in the SoA. Participants who are unwilling or unable to wait until Week 48 will have the biopsy procedure as part of the early discontinuation visit if they have received study intervention for at least 36 weeks. Samples for clinical safety laboratory assessments, amylase and lipase, coagulation parameters, and calcitonin do not need to be collected at visits occurring more than 30 days after discontinuation of study intervention except as needed for lab abnormalities/AEs that require follow-up to resolution.

Note that discontinuation from study intervention is NOT the same thing as a withdrawal from the study.

An individual participant will not receive any further IP if any of the following occur:

- Withdrawal of consent/assent from further treatment with IP.
- Lost to follow-up.
- Noncompliance that, in the opinion of the investigator or sponsor, warrants withdrawal (eg, refusal to adhere to scheduled visits).
- Pregnancy in a female participant.
- An AE that, in the opinion of the investigator or the sponsor, contraindicates further dosing; specific examples include:
  - Clinically significant tachyarrhythmias, including but not limited to life-threatening arrhythmia, eg, sustained ventricular tachycardia or ventricular fibrillation.
  - Acute pancreatitis

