#### 9.4.1 General Considerations

The primary analyses will be of safety. No formal hypothesis testing will be performed. Treatments will be compared in tables using descriptive statistics.

Exploratory efficacy analyses will use nominal 2-sided 5% significance levels (equivalent to nominal 1-sided 2.5% significance levels) unless otherwise stated.

The primary estimand of interest for the histological endpoints will use the treatment policy strategy. The treatment policy approach applies to intercurrent events of treatment discontinuation, deviations from the protocol titration schedule, changes in background medication, liver events, or use of prohibited medication or other protocol deviations. The treatment policy strategy will also be used to handle the intercurrent events for continuous endpoints.

Participants will be analyzed according to their randomized IP assignment and dose, irrespective of the treatment they actually received. Analyses will be performed using the FAS and/or per protocol analysis sets, as appropriate (Table 14). The FAS will include all randomized and treated participants who received at least one dose of IP irrespective of their protocol adherence, addition or modification of background medications, discontinuation of study intervention or switches to alternative medications, and continued participation in the study.

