# 9.4.2 Efficacy

The following exploratory endpoints will be analyzed descriptively versus placebo with 95% CIs at the nominal 2-sided alpha 5% level:

- Resolution of NASH at Week 48 without worsening of fibrosis
- Improvement in fibrosis at Week 48 without worsening of NASH
- Resolution of NASH and improvement in fibrosis at Week 48
- Improvement in fibrosis by at least one stage at Week 48
- Change from baseline in triglycerides, LDL cholesterol, HDL cholesterol, non-HDL cholesterol, total cholesterol, and HbA1c through Week 48

Additional exploratory endpoints and their analyses will be detailed in the SAP.

The binary endpoint(s) will be analyzed using a Cochran-Mantel-Haenszel test with stratification by T2DM presence and F2/F3 fibrosis stages. The treatment effects will be summarized by the difference in proportions, 95% CI, and p-value. For the exploratory analysis of binary histological endpoints using FAS, participants with no liver outcome and missing histology data due to any reason may be imputed as non-responders.

Continuous endpoints (absolute change in body weight, change in HbA1c, percent change in triglycerides) will be analyzed using Analysis of Covariance models, adjusting for baseline value, presence of T2DM, and fibrosis stage (F2/F3). For the primary analyses of these endpoints, missing data will be imputed via multiple imputations.

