## 3.3.2 Visit Window

For the purpose of the statistical analysis, study findings are allocated to the analysis visit using analysis visit windows as described in Table 2, Table 3, Table 4, Table 5, Table 6, Table 7, and Table 8. Note, study day 1 refers to the date the participant received the first dose of IP.

Table 2 Analysis Visit Windows, Biopsy

Analysis Visit	Target Day	Day Range
Week 48	337	1 through end of study

Table 3 Analysis Visit Definitions, 12-lead dECG, Vital Signs, Abbreviated Physical Examination

Analysis Visit	Target Day	Day Range
Week 4	29	2-42
Week 8	57	43-70
Week 12	85	71-98
Week 16	113	99-126
Week 20	141	127-154
Week 24	169	155-196
Week 32	225	197-252
Week 40	281	253-308
Week 48	337	309-351
Week 52	365	352-385

dECG, digital electrocardiogram.

Table 4 Analysis Visit Definitions, Clinical Laboratory Assessments Including eGFR and MELD but Excluding Fasting Glucose (Safety)

Analysis Visit	Target Day	Day Range
Week 4	29	2-42
Week 8	57	43-70
Week 12	85	71-98
Week 16	113	99-126
Week 20	141	127-154
Week 24	169	155-196
Week 32	225	197-280

Table 4 Analysis Visit Definitions, Clinical Laboratory Assessments Including eGFR and MELD but Excluding Fasting Glucose (Safety)

Analysis Visit	Target Day	Day Range
Week 48	337	281-351
Week 52	365	352-385

Due to fasting at the Week 48 visit, random glucose will not be presented for the Week 48 analysis visit. eGFR, estimated glomerular filtration rate; MELD, model for end-stage liver disease.

Table 5 Analysis Visit Definitions, Amylase, Lipase, Coagulation

Analysis Visit	Target Day	Day Range
Week 24	169	2-196
Week 32	225	197-280
Week 48	337	281-378

Table 6 Analysis Visit Definitions, Calcitonin, FibroScan, FAST, Agile 3+, BARD, Fasting Serum Lipid Panel, ELF, Pro-C3, FIB-4, Fasting Plasma Glucose (Efficacy), Fasting Glucose (Safety), C-peptide, Adiponectin

Analysis Visit	Target Day	Day Range
Week 48	337	2-378

BARD, BMI, AST/ALT ratio, diabetes; ELF, enhanced liver fibrosis; FAST, FibroScan-ALT; FIB-4, fibrosis-4; Pro-C3, released N-terminal propeptide of type III collagen.

Table 7 Analysis Visit Definitions, PK, and ADA

Analysis Visit	Target Day	Day Range
Week 4	29	2-57
Week 12	85	58-127
Week 24	169	128-253
Week 48	337	254-378

ADA, anti-drug antibody; PK, pharmacokinetic(s).

Table 8 Analysis Visit Definitions, HbA1c, Urine Albumin, Creatinine

Analysis Visit	Target Day	Day Range
Week 12	85	2-127
Week 24	169	128-253
Week 48	337	254-378

HbA1c, hemoglobin A1c.

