## 4.2.3.4 Primary Analysis of Other Endpoints

Unless otherwise indicated, analyses of tertiary/exploratory histological endpoints and continuous exploratory endpoints at Week 48 will include both on- and off-treatment measurements while analyses of endpoints at multiple timepoints through Week 48 will only include on-treatment measurements. The treatment effect for binary exploratory endpoints will be analyzed by the Cochran-Mantel-Haenszel (CMH) test, stratified for T2DM presence and F2/F3 fibrosis stages. The difference in proportion (unstratified response difference) with Miettinen-Nurminen (ie, score-based; without stratification) 95% confidence interval, and nominal p-value from CMH chi-square test will be provided.

Continuous endpoints summarized for a single post-baseline timepoint (Week 48) will be analyzed using ANCOVA with baseline, baseline T2DM status, baseline fibrosis stage, and treatment as independent variables, using multiple imputation. If an issue is encountered for fitting an ANCOVA model (eg, collinearity with intercept), a simplified model may be used. For analysis of (absolute) change from baseline, endpoints will be analyzed without transformation and LSMEAN change from baseline by treatment; the treatment effect as the LSMD will be reported as point estimates and 95% confidence intervals with p-values provided for treatment effect. For analysis of percent change from baseline, ANCOVA will be performed using log-transformed values. Point estimates and 95% confidence intervals of percent change from baseline by treatment and ratio change from baseline will be reported with a nominal p-value for treatment effect (Section 4.2.3.2). Rubin's rules (Rubin 1987) will be used to pool LSMEAN and LSMD values and associated standard errors across multiply imputed datasets and will provide the reported estimates and p-values. The following variables will be log-transformed: ALT, AST, APRI, triglycerides, PRO-C3, FIB-4, FPG, (total and high molecular weight) adiponectin, and C-peptide. Other variables may be log-transformed if required.

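### Missing Week 48 body weight is imputed within arm without regard to whether the participant had stopped study drug, and no planned analysis tests what this does to the treatment-policy estimate

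*SAP*

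**What the plan says.** Protocol 9.4.1, after listing stopping treatment among the intercurrent events, states: "The treatment policy strategy will also be used to handle the intercurrent events for continuous endpoints". For missing continuous data, Protocol 9.4.2 says only that "missing data will be imputed via multiple imputations", without a mechanism.

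SAP 4.2.3.4 is in line with treatment policy for observed data: analyses of "continuous exploratory endpoints at Week 48 will include both on- and off-treatment measurements". For a missing value at a single post-baseline timepoint, SAP 4.2.3.3 specifies that it is "imputed using multiple imputation (monotone regression) separately by randomized treatment arm with stratification variables (baseline fibrosis stage and T2DM status) and baseline measurement" for that endpoint. No term identifies participants who had stopped IP. SAP 4.2.3.5, on additional analyses, reads None.

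Three other provisions decide who is imputed:

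- **Follow-up.** Protocol 7.1 says of those who stop IP early that "participants will be encouraged to remain in the study for all remaining visits and study procedures as outlined in the SoA". Safety laboratory samples, however, "do not need to be collected at visits occurring more than 30 days after discontinuation of study intervention".
- **Body weight window.** The schedule of activities measures weight within the abbreviated physical examination. SAP 3.3.2 Table 3 ("Analysis Visit Definitions, 12-lead dECG, Vital Signs, Abbreviated Physical Examination") sets Week 48 as Days 309-351.
- **Table 6 window.** Most other single-timepoint markers use Days 2-378, so an early discontinuation value is taken as Week 48 and nothing is imputed.

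SAP 3.3 repeats the treatment-policy text for histology but omits the protocol's sentence on continuous endpoints. SAP Section 2 reports no change from the protocol other than to the per-protocol set.

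**The concern.** Under treatment policy, a participant who stopped cotadutide and left should contribute the Week 48 weight they would have had off drug. The imputation model cannot represent that. It draws the value from everyone observed in the arm, who are likely to be mostly still on drug, adjusted only for baseline weight, fibrosis stage and T2DM. If weight returns toward its untreated course after stopping, a benefit that was lost is put back. In placebo there should be little to put back, so the between-arm difference would be inflated.

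The documents make such dropout plausible. Protocol 2.2.2 reports more nausea and vomiting on cotadutide than on placebo. Protocol 6.6 has participants who cannot reach 200 µg stop IP. The titration schedule places that step at Week 8, so some could be off drug for about 48 - 8 = 40 weeks by Week 48.

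What is at stake is the exploratory objective on superiority for weight reduction. Three other endpoints may be exposed:

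- APRI and NFS, which are absent from Table 6 and rest on safety laboratory values that need not be drawn long after stopping.
- Continuous AI histology scores, if analysed by ANCOVA, because participants with under 36 weeks on IP have no biopsy at the early discontinuation visit.

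**Working it through.** **The plan's own figure.** The documents give no figure for continuous endpoints. The only sizing claim is more than 90% power for NASH resolution at 100 versus 100, 35% versus 15%, two-sided 0.05. It reproduces at 91.0% and has no bearing here.

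**Inputs.** Set the effect on drug to 1 and assume no on/off difference in placebo. Let d be the share of the cotadutide arm that stops IP, r the share of stoppers with a Week 48 value, and k the share of the effect kept off drug. None of these is in the documents; all are assumptions. Missingness is taken to come only from stoppers. Arm size: 55 × 2/6 = 18.3 per cotadutide arm.

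**Formulas.**

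- Treatment-policy effect: TP = (1-d) + dk
- SAP within-arm imputation: S = [(1-d) + drk] / [(1-d) + dr]
- Placebo-based imputation of unmeasured stoppers: P = (1-d) + drk

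It follows that S - TP = (1-d)·d·(1-r)(1-k) / [(1-d) + dr], which is positive whenever some stoppers are unmeasured and some effect is lost. Also P - TP = -d(1-r)k, which is zero or negative. Under these assumptions S and P bracket the treatment-policy effect.

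| d | r | k | TP | S (SAP) | P (placebo-based) | S/TP - 1 |
|---|---|---|---|---|---|---|
| 10% | 50% | 0.5 | 0.950 | 0.974 | 0.925 | 2.5% |
| 20% | 30% | 0.25 | 0.850 | 0.948 | 0.815 | 11.5% |
| 20% | 0% | 0 | 0.800 | 1.000 | 0.800 | 25% |
| 30% | 50% | 0.5 | 0.850 | 0.912 | 0.775 | 7.3% |
| 30% | 50% | 0 | 0.700 | 0.824 | 0.700 | 17.6% |
| 30% | 0% | 0 | 0.700 | 1.000 | 0.700 | 43% |

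Worked line, second row: TP = 0.80 + 0.20×0.25 = 0.85. S = (0.80 + 0.20×0.30×0.25)/(0.80 + 0.20×0.30) = 0.815/0.86 = 0.948. Ratio 0.948/0.85 = 1.115.

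**How far toward the stayed-on-drug effect.** (S - TP)/(1 - TP) = (1-d)(1-r)/[(1-d) + dr]. At r = 0 this is 100%. For d = 10-40% it is 47% down to 38% at r = 50%, and 23% down to 17% at r = 75%.

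**Against sampling error.** The SAP's imputation and ANCOVA were simulated with an assumed on-drug weight effect of -8 points, SD 7, 18 versus 18 with pooled placebo as one group, equal stopping in both arms, 1,500 runs and 10 imputations:

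- 20% stopping, none measured, no effect kept: truth -6.4, estimate -8.05.
- 20% stopping, half measured, no effect kept: truth -6.4, estimate -7.18.
- 30% stopping, half measured, no effect kept: truth -5.6, estimate -6.54.

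Over six cases the bias was 0.51 to 1.67 points, against a standard deviation of the estimate of 2.69 to 3.12.

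**The case against.** The strongest reply is that treatment policy governs intercurrent events, while missing data is a separate assumption on which the protocol asks only for multiple imputation. The SAP therefore does not contradict the protocol's text. It keeps off-treatment Week 48 values, those values also inform the imputation model, and stoppers are encouraged to stay. This stands against a reading that a reader might infer, that the analysis swaps treatment policy for a hypothetical estimand. The estimate reaches the stayed-on-drug effect only if no stopper has a Week 48 value; otherwise it lies between the two.

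A reader might also infer that Week 48 endpoints in general are affected. They are not. Table 6 endpoints use the discontinuation-visit value, which raises a different question, and endpoints analysed over several visits are not imputed.

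The direction is conditional too. No dropout rate, retention rate or off-drug course is given, and the 43% case needs every stopper to leave and all effect to vanish. All p-values are nominal, and the simulated bias is below one standard error.

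Finally, placebo-based imputation can err more than the present method. At d = 30%, r = 50%, k = 0.5 it gives 0.775 against a true 0.85, an error of -0.075, while the SAP method gives 0.912, an error of +0.062. That is a fair argument against replacing the main analysis. It does not answer the absence of any check.

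**Conclusion.** The point holds for percent change in body weight at Week 48, and possibly for APRI, NFS and continuous AI histology scores. The imputation assumes missing at random within arm regardless of IP status, which fits poorly with treatment policy for participants who stopped and left, and nothing planned tests it.

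The overstatement is about 2.5% to 43% over d = 10-30%, r = 0-50% and k = 0-0.5. It is 11.5% and 17.6% in the two mid-range cases (20% stopping, 30% measured, 25% of effect kept; 30% stopping, half measured, none kept). With good retention it is small: 1.2% at d = 10%, r = 75%, k = 0.5.

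The sign depends on the effect waning off drug and on placebo having no on/off difference. Both are plausible; neither is shown in the documents. The body weight window rests on reading Table 3's physical examination label together with the schedule of activities. The documents do not support a claim that the weight result will be biased in cotadutide's favour, or that its p-value will be too small by a known amount.

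**What to change.** In SAP 4.2.3.3 and 4.2.3.5:

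1. State that the current imputation assumes missing at random within arm, whatever the IP status.
2. For body weight and any other affected endpoint, pre-specify a second multiple imputation. Participants who stopped IP and lack a Week 48 value are imputed from pooled placebo; those still on IP keep the arm-based imputation.
3. Report the two results side by side as the range for the treatment-policy effect, with counts by arm of stoppers with and without a Week 48 value.
4. Restore the protocol's continuous-endpoint sentence in SAP 3.3, and state which visit window applies to body weight, APRI and NFS.

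Imputing from stoppers who were measured would be closer to the estimand but is rarely workable: 30% stopping with half measured leaves 18 × 0.30 × 0.50 = 2.7 donors per cotadutide arm.

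The cost is some SAP wording and one extra analysis before unblinding; IP stop dates are already in the eCRF (Protocol 6.4). The placebo-based estimate will be smaller than the current one if cotadutide reduces weight, and is conservative if the effect persists off drug, so it belongs beside the current analysis and not in its place.
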